1.9 Evaluation of ABT-414 in Children with High Grade Gliomas

[Appendix I](#) provides information related to the evaluation of ABT-414 in children (M14-483 pediatric sub-study). Unless specifically addressed in [Appendix I](#), all of the adult protocol elements will apply to the pediatric population.

Background: Pediatric high grade gliomas [HGG] (WHO grade III and IV glioma and diffuse intrinsic pontine glioma [DIPG]) have no adequate therapy and are almost universally fatal. Unlike in adult GBM, EGFR amplification is rare (3% or lower) in pediatric HGG and screening for EGFR amplification is not routinely part of standard care for pediatric tumors, which makes it profoundly difficult to identify children with EGFR amplified HGG. Consequently, it is not feasible to conduct a stand-alone study in this population. It is most important that a pediatric study in EGFR-amplified HGG addresses whether a proposed dose of ABT-414 can be used safely in the pediatric population, with recognition that assessment of efficacy beyond a description of outcomes in a very small number of subjects is likely infeasible.

2 Objectives of the trial

2.1 General objectives

The objectives of the trial are to assess whether ABT-414 alone or in combination with TMZ improves overall survival (OS), PFS, tumor response, quality of life, NDFS and steroid use compared to standard treatment with lomustine single agent or TMZ re-challenge in patients with centrally confirmed recurrent EGFR-amplified glioblastoma.

Additional exploratory objectives include analyses by stratum of EGFR pathway abnormalities (specifically EGFRvIII mutation), correlation of MGMT methylation status with clinical outcome (PFS/OS), and exploratory clinical and translational research program.

The objectives will be achieved within a testing strategy, which aims to preserve the global type I error. The objectives will be realized according to the following hierarchical sequence: OS, PFS, response, OS in EGFRvIII mutated. Secondary objectives not included in the testing sequence will be realized for exploratory purpose.

2.2 End-points

2.2.1 Primary endpoint

The primary endpoint will be OS at final analysis and Progression Free Survival (PFS) according to RANO criteria and assessed by IRC at the interim analysis.

2.2.2 Secondary endpoints

Secondary endpoints will be:

- PFS according to RANO criteria and assessed by IRC
- Objective response rate (ORR) assessed by IRC
- OS in the subgroup with EGFRvIII mutation

The following are exploratory endpoints:

- Best overall response rate (BOR), complete response rate (CRR), duration of response (DR) assessed by IRC will be computed in each arm
- PFS in the subgroup with EGFRvIII mutation
- Neurological deterioration-free survival (NDFS)

- Steroid use
- Frequencies and percentages of worst Adverse Events (AEs) or Laboratory Event grades
- Quality of life

3 Patient selection criteria

Patients with histologically confirmed *de novo* (primary) glioblastoma may register and have their tumor tissue screened after diagnose and before tumor progression. Eligibility at the time of tumor progression will depend on the confirmation of EGFR amplification during the screening, the fulfillment of all other patient selection criteria and the trial status (whether the study is still open for accrual).

For patients < 18 years old, please refer to the inclusion criteria listed in [Appendix I](#)

3.1 Registration

- Histologically confirmed *de novo* (primary) glioblastoma before or at the time of first progression after RT concurrent/adjuvant TMZ chemotherapy.
 - In case of testing at the time of first progression: either at least 3 months after the end of radiotherapy or have tumor progression that is clearly outside the radiation field or have tumor progression unequivocally proven by surgery/biopsy
- Age \geq 18 years
- Absence of any psychological, familial, sociological or geographical factors potentially hampering compliance with the study protocol and follow-up schedule; such conditions should be assessed with the patient before registration in the trial.
- Availability of adequate biological material (formalin-fixed paraffin embedded [FFPE] tumor) for central testing of EGFR amplification
- Written informed consent for central EGFR screening must be given according to ICH/GCP, and national/local regulations.

3.2 Randomization

The following criteria should be assessed within 2 weeks prior to randomization.

- Histologically confirmed *de novo* (primary) glioblastoma with unequivocal first progression after RT concurrent/adjuvant TMZ chemotherapy either at least 3 months after the end of radiotherapy or have tumor progression that is clearly outside the radiation field or have tumor progression unequivocally proven by surgery/biopsy
- Presence of EGFR amplification confirmed by central assessment; patients with undetermined EGFR status are excluded
- WHO Performance status 0 - 2 (see [Appendix C](#))
- No prior treatment with nitrosoureas
- No prior treatment with bevacizumab
- No previous exposure to EGFR targeted agents, including EGFRvIII targeting agents and participation to placebo controlled trials on EGFR targeted agents
- No prior discontinuation of temozolomide chemotherapy for toxicity reasons
- No more than one line of chemotherapy for GBM (concurrent and adjuvant TMZ based chemotherapy including in combination with another investigational agent is considered one line of chemotherapy). Chemotherapy must have been completed at least 4 weeks prior to randomization.
- No prior RT with a dose over 65 Gy to the brain, stereotactic radiosurgery or brachytherapy unless the recurrence is histologically proven

- No previous other malignancies, except for any previous malignancy which was treated with curative intent more than 5 years prior to randomization, and except for adequately controlled limited basal cell carcinoma of the skin, squamous carcinoma of the skin or carcinoma *in situ* of the cervix
- Absence of known hypersensitivity
 - to any part of the ABT-414 compound, TMZ, dacarbazine or lomustine formulations
 - to any IgG containing agent
- No history of Coeliac disease and wheat allergy
- Patient may have been operated for recurrence. If operated:
 - residual and measurable disease after surgery is not required but surgery must have confirmed the recurrence
 - a post-surgery MRI must be available within 48 hours following surgery, however an MRI scan has to be done within 2 weeks prior to randomization
 - surgery completed at least 2 weeks before randomization and patients should have fully recovered as assessed by investigators. Criteria for full recovery will include absence of active post-operative infection, recovery from medical complications and capacity for fluid and food intake.
- For non-operated patients, recurrent disease must include at least one bi-dimensionally measurable contrast-enhancing lesion with clearly defined margins by MRI scan, with minimal diameters of 10 mm, visible on 2 or more axial slices 5 mm apart, based on an MRI scan done within 2 weeks prior to randomization
- Stable or decreasing dosage of steroids for 7 days prior to the baseline MRI scan
- No current or recent (within 4 weeks before randomization) treatment with another investigational drug
- Patients who require anti-convulsant therapy must be taking non-enzyme inducing antiepileptic drugs (non-EIAED). Patients previously on EIAED must be fully switched to non-EIAED at least 2 weeks prior to randomization
- No underlying or previous conditions that could interfere with treatment, including but not limited to:
 - no evidence of active infection requiring hospitalization or antibiotics, within 2 weeks prior to randomization
 - no active infectious keratitis
 - no other diseases interfering with follow up
- No planned vaccinations with live vaccines
- Adequate hematological function defined as: neutrophils $\geq 1.5 \times 10^9$ cells/L and platelets $\geq 100 \times 10^9$ cells/L and hemoglobin ≥ 6.2 mmol/L (9.9 g/dl)
- Normal liver function: bilirubin $< 1.5 \times$ upper limit of the normal range (ULN), alkaline phosphatase and transaminases (ASAT) $< 2.5 \times$ ULN
- Renal function: calculated creatinine clearance ≥ 30 mL/min by the Cockcroft-Gault formula (see [Appendix E](#))
- Absence of pregnancy. Women of childbearing potential (WOCBP) must be using an adequate method of contraception to avoid pregnancy throughout the study and for 6 months beyond the end of treatment in such a manner that the risk of pregnancy is minimized. In general, the decision for appropriate methods to prevent pregnancy should be determined by discussions between the investigator and the study subject. WOCBP include any female who has experienced menarche and

who has not undergone successful surgical sterilization (hysterectomy, bilateral tubal ligation, or bilateral oophorectomy) or is not postmenopausal. Females should not be breastfeeding.

- Post menopause is defined as: amenorrhea ≥ 12 consecutive months without another cause or for women with irregular menstrual periods and on hormone replacement therapy (HRT), a documented serum follicle stimulating hormone (FSH) level > 35 mIU/mL
- Women who are using oral contraceptives, other hormonal contraceptives (vaginal products, skin patches, or implanted or injectable products), or mechanical products such as an intrauterine device or barrier methods (diaphragm, condoms, spermicide) to prevent pregnancy, or are practicing abstinence or where their partner is sterile (e.g., vasectomy) should be considered to be of childbearing potential.
- Women of childbearing potential must have a negative serum or urine pregnancy test (minimum sensitivity 25 IU/L or equivalent units of HCG) within 72 hours prior to randomization.
- Female patients within one year of entering the menopause must agree to use an effective non-hormonal method of contraception during the treatment period and for at least 6 months after the last study treatment.
- Males must agree to use an effective method of contraception during the treatment period and for at least 6 months after the last study treatment.
- Before patient randomization and study related procedures (that would not have been performed as part as standard care), written informed consent must be given according to ICH/GCP, and national/local regulations.
- Patients with a buffer range from the normal values of $\pm 5\%$ for hematology and $\pm 10\%$ for biochemistry are acceptable. A maximum of ± 2 days for timelines are acceptable (with the exception of the pregnancy test).

Important note: All eligibility criteria must be adhered to, in case of deviation discussion with Headquarters and study coordinator is mandatory.

4 Study Procedures

This is a randomized open label multicenter phase II trial (see objectives in chapter 2).

For detailed statistical considerations, see chapter 8.

Patients will be randomized at the EORTC headquarters **after verification of the eligibility criteria (see chapter 3)** to receive one of the following:

Arm 1: patients will be treated with ABT-414 1.0 mg/kg IV infusion over 30 to 40 minutes once every 2 weeks in combination with TMZ 150 mg/m² day 1 to 5, for the first 28-day cycle, with dose escalation to 200 mg/m² in subsequent cycles in case of adequate tolerance and until one of the treatment withdrawal criteria has been met. In this Arm 1 the schedule of clinical and lab assessments follows the cycle of TMZ (a delay of TMZ delays the assessment schedule, withholding ABT-414 does not affect the assessment schedule).

Arm 2: patients will be treated with ABT-414 monotherapy 1.0 mg/kg IV infusion over 30 to 40 minutes once every 2 weeks until one of the treatment withdrawal criteria has been met.

Arm 3: Patients in the control arm will be treated according to the timing of relapse.

Arm 3A: Patients relapsing during TMZ treatment or within the first 16 weeks after the first day of the last TMZ cycle will be treated with lomustine 110 mg/m² on day 1 of every 42-day treatment period.

Treatment will continue until one of the treatment withdrawal criteria has been met. Lomustine will be given for a maximum of one year.

Arm 3B: Patients relapsing 16 weeks or more after the first day of the last TMZ cycle will be treated with TMZ 150 mg/m² on day 1 to 5 for the first 28-day cycle, with dose escalation to 200 mg/m² in subsequent cycles in case of adequate tolerance. Treatment will continue until one of the treatment withdrawal criteria has been met.

[figure not shown]
Treatment should start within 96 hours from randomization.

Treatment at further progression will be according to investigators discretion. Day 1 of the first cycle will be the first day when the study medication is taken.

There will be an interim futility analysis organized. At interim analysis one or both of the ABT-414 arms might be discontinued based on lack of efficacy for PFS (Reject H1 in favor of H0) according to RANO criteria assessed by IRC (see section 8.3).

Disease will be assessed by study-specific MRI according to the study specific imaging protocol every 8 weeks. Response and progression will be assessed by the RANO criteria (see section 7.1).

The safety profile will be assessed separately for each cycle of therapy with CTCAE v4 (see section 7.2).

5 Therapeutic regimens, expected toxicity, dose modifications

5.1 General information

5.1.1 ABT-414

Guidelines for ABT-414 dose preparation, volume, and rate of infusion will be supplied by AbbVie to the site staff, within the study manual.

5.1.1.1 Drug supplies

Drug supplies and re-supplies will be provided free of charge by AbbVie as long as patients are on protocol treatment (for procedures: see study manual that will be provided at the time of activation).

The investigator should ensure that the investigational product is stored in accordance with the environmental conditions (temperature, light, and humidity) as determined by AbbVie. If concerns regarding the quality or appearance of the investigational product arise, do not dispense the investigational product and contact AbbVie immediately. Pharmacy and clinic personnel should wear disposable chemotherapy gloves. Pregnant personnel should avoid exposure to the medication.

5.1.1.2 Packaging, dispensing and storage

Medication labels will comply with the legal requirements as applicable and will be printed in the local language. The storage conditions for study drug will be described on the medication label.

5.1.1.3 Drug reconciliation procedures

Accountability of the investigational study drug(s) is under the responsibility of the investigator and can be delegated to an appropriately qualified person.

The Investigator or representative will verify that study drug supplies are received intact, at the appropriate temperature and in the correct amounts. This will be documented by signing and dating the Proof of Receipt or similar document or via direct recording in the Interactive response technology (IRT)

An overall accountability of the study drug will be performed and verified by the AbbVie monitor throughout the study and at the study site closeout visit. An accurate running inventory of study drug will be maintained utilizing the IRT drug accountability module and, if required, according to your institutional policy, which should include the lot number, POR number(s), the bottle/kit numbers, and the date study drug was dispensed for each subject.

In the event that the IRT is not operable, the above information will be documented on forms provided by the Sponsor.

After verification of drug accountability, used/empty vials may be destroyed at the site according to local regulations governing biohazardous waste. Destruction of used study supplies must be documented. All unused study drug unit doses must be inventoried, accounted for, and returned to AbbVie or destroyed per instructions from AbbVie and according to local regulations. A copy of the Return Shipment Form, in accordance with instructions provided by the AbbVie monitor, will also be included in the shipment.

Labels must remain attached to the containers. If pre-arranged between AbbVie and the site, destruction of the study drug may be performed at the site.

In addition to internal accountability documentation on site, EORTC/AbbVie study-specific accountability and drug destruction forms will be supplied for this purpose, if site-specific forms are deemed not

sufficiently detailed or do not provide enough information, according to EORTC Quality Assurance criteria.

The medication provided for this trial is to be used only as indicated in this protocol and only for the patients entered in this study.

5.1.2 Lomustine

Lomustine is considered as a standard treatment in many countries for this indication and commercial sources will be used. The exception will be in countries where Lomustine is not available commercially or in countries which mandate sponsor to supply drugs within the context of clinical trials. For those countries, AbbVie may provide or reimburse for Lomustine to participating sites as required based upon availability or local regulations.

5.1.3 Temozolomide (TMZ)

TMZ is considered as a standard treatment for this indication and commercial sources will be used, except in countries which mandate Temozolomide be supplied by the sponsor in the context of clinical trials. For those countries, AbbVie may provide or reimburse for TMZ to participating sites as required based upon availability or local regulations.

5.2 Initial dose and administration

5.2.1 ABT-414

ABT-414 will be given at dose level of 1.0 mg/kg by IV infusion over 30 to 40 minutes once every 2 weeks. The dose of ABT-414 does not have to be adjusted unless there has been at least a 10% change in body weight; recalculation of ABT-414 dose for < 10% weight changes is allowed at the discretion of the Investigator. Each configuration of ABT-414 drug product (Type A and/or Type L) that a subject receives during the study will be recorded.

Subjects will be closely monitored for treatment-related adverse events, especially allergic reactions, during the infusion. For the initial ABT-414 infusion, pre-infusion vital signs should be taken, direct observation is required for the first 15 minutes of the infusion, and subjects should be monitored for 1 hour post-infusion. For subsequent infusions, direct observation and monitoring post-infusion are not required; however, pre-infusion vital signs should still be taken.

Due to the risk of eye toxicity, each administration of ABT-414 should be given with steroid ophthalmic solution. The recommended type, dose, and schedule of eye drops is as follows: dexamethasone 0.1% solution (or equivalent corticosteroid solution), 2 drops (GTTS) in each eye (OU) every 8 hours to start 48 hours prior to ABT-414 dosing and continue for a total of 7 days (or 21 doses total). The type of ophthalmic solution used may vary depending on the availability of the solution at each location. A modification to the eye drop dosing or schedule based on ongoing clinical experience may be suggested.

Allergic reactions of any grade require interruption of ABT-414 treatment and management as described in section [5.5.1.1](#).

Subjects will not be treated at doses less than 0.5 mg/kg. If a subject requires a dose modification below 0.5 mg/kg, the subject will be discontinued from the study treatment.

5.2.2 Lomustine

Arm 3A: Patients relapsing during TMZ treatment or within the first 16 weeks after the first day of the last TMZ cycle will be treated with lomustine 110 mg/m² on day 1 of every 42-day treatment period. However, similar to subjects who are randomized to ABT-414 plus TMZ (Arm 1), ABT-414 (Arm 2) or TMZ control (Arm 3B), scans (MRI) should be performed as per the schedule outlined for all other arms (see section 6.3.5). Treatment will continue until one of the treatment withdrawal criteria has been met. Lomustine will be given for a maximum of one year.

The doses may be rounded to the nearest 40 mg to accommodate tablet strengths. The dose of lomustine does not have to be adjusted unless there has been at least a 10% change in body weight; recalculation of lomustine dose for < 10% weight changes is allowed at the discretion of the Investigator.

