5.5.2.1 Dose levels of lomustine

The lomustine dose will be rounded to the closest multiple available; the dosage is calculated based on BSA but a maximum dose (cap) is used. Two dose levels of lomustine will be used.

Dose	Dose mg/m ² q6 weeks
0	110 mg/m ² (cap 200 mg)
-1	90 mg/m ² (cap 160 mg)
-2	70 mg/m ² (cap 120 mg)

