5.5.2.1.1 Hematological toxicity

In general, the nadirs for hematological toxicity with lomustine are expected between days 28 and 35. In case of hematological toxicity grade 3 or 4 (according to CTCAE v. 4.0), the dosage of the next cycle will be reduced with one level. If the hematological toxicity does not recover within 4 weeks or if after recovery the hematological toxicity recurs at a subsequent cycle to grade ≥ 2 , lomustine treatment should be discontinued. No more than two dose reductions are allowed.

Administration of next cycle: If blood examination on day 42 or 43 (which may have been obtained in the prior 48 hours) show recovery of platelets above 100×10^9 and granulocytes counts above 1.5×10^9 , the next dose may be administered on day 43. If this is not possible, hematologic parameters will be repeated weekly and the next cycle will be given upon recovery of granulocytes and platelets. If after 4 weeks the patient has still not recovered, they should discontinue study treatment and stay on study until progression.

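### Where a site uses the permitted 40 mg rounding, a required one-level lomustine reduction can leave the administered dose unchanged at some body surface areas

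*Protocol*

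**What the plan says.** The protocol deals with lomustine rounding in two places.

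- Section 5.2.2, on initial dose and administration: "The doses may be rounded to the nearest 40 mg to accommodate tablet strengths".
- Section 5.5.2.1, on dose levels: "The lomustine dose will be rounded to the closest multiple available; the dosage is calculated based on BSA but a maximum dose (cap) is used". No step size is given there.

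The table in section 5.5.2.1 lists level 0 at 110 mg/m² (cap 200 mg), level -1 at 90 mg/m² (cap 160 mg) and level -2 at 70 mg/m² (cap 120 mg). The sentence above the table reads "Two dose levels of lomustine will be used", although three rows follow.

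After grade 3 or 4 hematological toxicity, section 5.5.2.1.1 requires that "the dosage of the next cycle will be reduced with one level". Section 5.5.2.1.2 requires a one-level reduction for liver toxicity above grade 2, but stops treatment for any grade 4 non-hematological toxicity, so its liver reduction applies to grade 3. At most two reductions are allowed (sections 5.5.2 and 5.5.2.1.1). Recurrence of toxicity at grade 2 or worse leads to stopping, under separate rules for hematological and non-hematological toxicity.

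**The concern.** One level is worth 20 mg/m². Below a BSA of 2.0 m² that is less than 40 mg (20 × 2.0 = 40), so rounding to the nearest 40 mg can put two adjacent levels on the same number of milligrams. Nothing in the documents requires the rounded reduced dose to be lower than the dose before it.

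A site could then carry out a safety instruction exactly, record a reduction, and give the same amount as before. That step would still use up one of the two reductions. If hematological toxicity then recurred at grade 2 or worse, lomustine would be stopped although the milligram dose had never fallen. Because the two sections state the rounding differently, two sites could also give different amounts to patients of the same size at the same level. All of this concerns Arm 3A only, the part of the control arm that receives lomustine.

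**Working it through.** **Inputs.** Levels of 110, 90 and 70 mg/m² and caps of 200, 160 and 120 mg come from Protocol section 5.5.2.1. The 40 mg step is the one permitted in section 5.2.2. The documents give no table of administered milligrams to reproduce.

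**Formula.** Administered mg = min(cap, 40 × round(level × BSA / 40)). All three caps are multiples of 40, so capping before or after rounding gives the same result.

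**Breakpoints.** A dose rounds to 80 mg from 60 up to 100 mg, to 120 mg from 100 up to 140 mg, and to 160 mg from 140 up to 180 mg.

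- Level 0 gives 160 mg from 140/110 = 1.273 to 180/110 = 1.636 m², and 200 mg above that.
- Level -1 gives 120 mg from 100/90 = 1.111 to 140/90 = 1.556 m², and 160 mg above that.
- Level -2 gives 80 mg up to 100/70 = 1.429 m², and 120 mg above that.

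**Result.** A scan of BSA from 1.00 to 2.60 m² in steps of 0.0001 gives:

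| BSA (m²) | Level 0 / -1 / -2 (mg) | Reduction without effect |
|---|---|---|
| 1.00-1.111 | 120 / 80 / 80 | second |
| 1.111-1.273 | 120 / 120 / 80 | first |
| 1.273-1.429 | 160 / 120 / 80 | none |
| 1.429-1.556 | 160 / 120 / 120 | second |
| 1.556-1.636 | 160 / 160 / 120 | first |
| 1.636 and above | 200 / 160 / 120 | none |

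**Two examples.**

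- BSA 1.60 m²: 110 × 1.60 = 176, 90 × 1.60 = 144 and 70 × 1.60 = 112 mg, which round to 160, 160 and 120 mg.
- BSA 1.50 m²: 165, 135 and 105 mg, which round to 160, 120 and 120 mg.

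**Source of the overlap.** As a contrast only, an assumed 10 mg step, which is not in the documents and is not proposed here, keeps the three levels distinct at every BSA scanned. The overlap therefore comes from the 40 mg step and not from the levels or the caps.

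**The case against.** The strongest reply is that the 40 mg rounding is optional. Section 5.2.2 says doses may be rounded, and it concerns the initial dose; the section that defines the reduced levels names no step. This stands. The effect arises only where a site applies 40 mg rounding to a reduced dose, so it would be wrong to say that the protocol cancels a reduction for every patient in the range. The permission remains in the text, however, and no other section excludes its use at a reduced level.

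Second, the two bands are not equally important. From 1.429 to 1.556 m² only the second reduction is lost. Because recurrence at grade 2 or worse usually leads to stopping, reaching a second reduction generally needs a different kind of toxicity, for example hematological first and liver later. This also stands. The direct case is the narrower band, 1.556-1.636 m². Repeat exposure there is limited in part, because blood counts must recover before the next dose.

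Third, a reader might want to state how many patients are affected. The documents give no BSA distribution. Under assumed normal distributions, the 1.556-1.636 m² band holds about 20% of patients (mean 1.65, SD 0.15), 13% (mean 1.75, SD 0.15) or 1.5% (mean 2.0, SD 0.18). That spread is too wide, and too dependent on the assumption, to report as a finding.

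Fourth, a reader might infer that the SAP's dose-modification tables or the control-arm toxicity results would be misleading. The documents do not support this. SAP section 9.1 does not say that a modification is counted from the recorded level. It tabulates subjects at each treated dose over time, and SAP section 9.2 does so by treatment course, including lomustine. Protocol section 6.3.2 collects lomustine administration data, so an unchanged dose should be visible. Safety is not formally compared between arms (Protocol section 8.2.3.7, SAP section 11.1).

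**Conclusion.** The inconsistency is real but conditional. Where the permitted 40 mg step is used, the first required reduction has no effect at BSA of about 1.556-1.636 m², and the second has none at about 1.429-1.556 m². The same pattern recurs below about 1.27 m². From 1.636 m² upward, and from 1.273 to 1.429 m², all three levels differ.

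The bands follow exactly from the protocol's own levels, caps and step; the only condition is that a site uses the step. The number of patients is unknown. For scale, 240 planned patients randomized 1:1:1 give 80 controls. If the 60% early-relapse figure in Protocol section 1.2 applied to them, about 48 (80 × 0.60) would receive lomustine. Only those who fall in a band, need the reduction concerned and attend a site using the 40 mg step would be affected. No efficacy test or sample-size figure is touched. The point merits correction because it concerns a safety instruction and is cheap to resolve.

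**What to change.** The sponsor should reconcile sections 5.2.2 and 5.5.2.1, together with the reduction rules in 5.5.2.1.1 and 5.5.2.1.2, into one rounding statement. That statement should be checked against the level table, so that the rounding allowance and the instruction to reduce by one level do not contradict each other. Which doses and which rounding step to use is for the sponsor to decide.

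The same edit can clarify "Two dose levels of lomustine will be used", which may simply mean two reduced levels, since the table has three rows and two reductions are allowed.

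The cost is a short protocol clarification. If the sponsor chose to change the step, dispensing might become slightly less convenient. No change to the SAP is needed on this account.
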